## 7.2 Study Rationale

Clinical evaluation of lenvatinib in combination with everolimus in subjects who have not received any chemotherapy for advanced disease is warranted based on the following:

- The currently available first-line therapies for RCC are unsatisfactory. These treatments do not induce durable tumor responses and virtually all patients experience progression of disease requiring initiation of another therapy.
- the importance of VEGF, FGF, and mTOR signaling in RCC
- the clinical experience with lenvatinib in metastatic clear cell RCC
- The lack of availability of data to demonstrate that combination therapy in treatment of metastatic nccRCC provides significant advantage over single agent therapy.

It is hypothesized that combinations of targeted agents may overcome the resistance to treatments with single agent therapy. By using an mTOR inhibitor (everolimus) in combination with a VEGFR inhibitor (lenvatinib), blockade could take place at two levels of the pathways activated in RCC and this may overcome an aspect of resistance that may develop through feedback mechanisms.

# 8 STUDY OBJECTIVES

## 8.1 Primary Objective

The primary objective of the study is to evaluate ORR, as assessed by the investigator, of lenvatinib in combination with everolimus in subjects with unresectable advanced or metastatic nccRCC who have not received any chemotherapy for advanced disease.

## 8.2 Secondary Objectives

The secondary objectives of the study are:

- To assess safety and tolerability of lenvatinib in combination with everolimus
- To evaluate PFS as assessed by the investigator

- To evaluate OS
- To assess the PK profiles of lenvatinib and everolimus during combination therapy in subjects with nccRCC

### **8.3 Exploratory Objectives**

The exploratory objectives of the study are:

- To explore ORR as assessed by independent imaging review (IIR)
- To explore PFS as assessed by IIR
- To explore clinical benefit rate (CBR) as assessed by the investigator and by IIR
- To explore disease control rate (DCR) as assessed by the investigator and by IIR
- To explore duration of response (DOR) as assessed by the investigator and by IIR
- To identify and explore tumor and blood biomarkers that correlate with clinical outcomes, including efficacy
- To explore the relationship of population PK derived exposure parameters to biomarker, safety, and efficacy data using a model-based approach

## **9 INVESTIGATIONAL PLAN**

### **9.1 Overall Study Design and Plan**

E7080-M001-221 is a single-arm, multicenter, Phase 2 study of lenvatinib in combination with everolimus (lenvatinib 18 mg/day + everolimus 5 mg/day) in subjects with unresectable advanced or metastatic nccRCC who have not received any chemotherapy for advanced disease. A Simon's Two-Stage Design will be implemented in approximately 31 enrolled subjects. Sixteen subjects will be enrolled in Stage 1. If there are at least 2 responders as assessed by ORR, the study will proceed to Stage 2, in which 15 more subjects may be enrolled. Otherwise, the study will stop early for futility. In the final analysis of 31 subjects, at least 6 responders are required to show a statistically significant improvement of ORR over historical control in the same patient population.

This study consists of three Phases: a Pretreatment Phase (Screening and Baseline Periods), a Treatment Phase (starting Cycle 1, Day 1), and a Posttreatment Phase (End of Treatment Visit and survival Follow-up).

### 9.1.1 Pretreatment Phase

The Pretreatment Phase will last no longer than 21 days and will include a Screening Period to establish protocol eligibility and a Baseline Period to confirm eligibility and establish disease characteristics prior to treatment.

#### 9.1.1.1 Screening Period

Screening will occur between Day -21 and Day -2. The purpose of the Screening Period is to obtain informed consent and to establish protocol eligibility. Informed consent will be obtained after the study has been fully explained to each subject and before the conduct of any screening procedures or assessments. Procedures to be followed when obtaining informed consent are detailed in [Section 5.3](#).

Subjects must have a histologically-confirmed diagnosis of nccRCC.

The Screening Disposition case report form (CRF) page must be completed to indicate whether the subject is eligible to participate in the study and to provide reasons for screen failure, if applicable.

#### 9.1.1.2 Baseline Period

The purpose of the Baseline Period is to establish disease characteristics prior to starting treatment, and to confirm protocol eligibility as specified in the inclusion/exclusion criteria. Results of baseline assessments must be obtained and reviewed by the investigator prior to the first dose of study drug, ie, Cycle 1 Day 1 (C1D1), to confirm eligibility. Baseline assessments will be performed on Day -1 or on C1D1 prior to treatment.

Subjects who complete the Baseline Period and meet the criteria for inclusion/exclusion ([Sections 9.3.1](#) and [9.3.2](#)) will begin the Treatment Phase.

### 9.1.2 Treatment Phase

The Treatment Phase will begin at the time of study drug administration on C1D1 and continue in 28-day (4-week) cycles until completion of the off-treatment assessments (within 30 days after the last study drug administration). Lenvatinib 18 mg/day and everolimus 5 mg/day will be administered orally. Subjects will undergo safety and efficacy assessments. Toxicity will be managed by treatment interruption, dose reduction and/or treatment discontinuation. Subjects who discontinue one of the study drugs due to its toxicities may continue to receive the other study drug as long as they demonstrate clinical benefit. Subjects will discontinue both study drugs at the time of confirmed disease progression, development of unacceptable toxicity, withdrawal of consent, or study termination by the sponsor.

### 9.1.3 Posttreatment Phase

The Posttreatment Phase will start at the End of Treatment Visit and will continue as long as the subject is alive or until the study subject withdraws consent. Subjects who discontinue study treatment before disease progression will continue to undergo tumor assessment every 8 weeks  $\pm$  1 week until documentation of disease progression or start of another anticancer therapy. Follow-up assessment for survival will be performed every 12 weeks  $\pm$  1 week.

## 9.2 Discussion of Study Design, Including Choice of Control Groups

This is a single-arm, multicenter, Phase 2 study of lenvatinib in combination with everolimus (lenvatinib 18 mg/day + everolimus 5 mg/day) in subjects with unresectable advanced or metastatic nccRCC who have not received any chemotherapy for advanced disease. The current treatment approach for patients with metastatic nccRCC mirror that of clear cell RCC due to lack of randomized data and consists of sequential administration of single agent therapies that target either the vascular endothelial growth factor (VEGF)/VEGF receptor (VEGFR) or mammalian target of rapamycin (mTOR) pathways. As discussed in [Section 7.1.4](#), combining everolimus (an mTOR inhibitor) with lenvatinib (a VEGFR inhibitor) could block the pathways activated in RCC at 2 levels and may overcome an aspect of resistance, which develops with single agent therapy. The combination of lenvatinib and everolimus is chosen based on robust results from Study 205.

The current study is designed to provide efficacy and safety data for lenvatinib in combination with everolimus in this patient population. A recently reported Phase 1b/2 study in RCC showed a response rate of 43.1% and median PFS of 14.6 months (95% CI 5.9-20.1). The primary objective of the study is to evaluate ORR. The efficacy and safety parameters being evaluated are commonly used in oncology trials.

## 9.3 Selection of Study Population

Approximately 31 subjects will be enrolled at approximately 8 sites in regions that include the United States. Subjects who do not meet all of the inclusion criteria or who meet any of the exclusion criteria will not be eligible to receive study drug.

### 9.3.1 Inclusion Criteria

Subjects must meet all of the following criteria to be included in this study:

1. Males or females age  $\geq$  18 years at the time of informed consent form.
2. Histologically confirmed nccRCC who have not received any chemotherapy for advanced disease. Subjects must have one of the following subtypes of nccRCC: papillary, chromophobe, collecting duct carcinoma (CDC), renal medullary carcinoma (RMC), or unclassified.
3. Radiologically measurable disease meeting the following criteria:

- a. At least 1 lesion of  $\geq 10$  mm in the longest diameter for a nonlymph node or  $\geq 15$  mm in the short axis diameter for a lymph node which is serially measurable according to Response Evaluation Criteria in Solid Tumors (RECIST v1.1) (Appendix 1) using computerized tomography (CT) or magnetic resonance imaging (MRI).
- b. Lesions that have had external beam radiotherapy (EBRT) or locoregional therapies such as radiofrequency (RF) ablation must show evidence of subsequent progressive disease (PD) (substantial size increase of  $\geq 20\%$ ) to be deemed a target lesion.
4. Eastern Cooperative Oncology Group (ECOG) (Appendix 2) performance status of 0 to 1.
5. Blood pressure (BP)  $\leq 140/90$  mmHg at Screening with or without antihypertensive medications and no change in antihypertensive medications within 1 week prior to C1D1.
6. Adequate renal function as evidenced by calculated creatinine clearance  $\geq 30$  mL/min according to the Cockcroft and Gault formula (Appendix 3).
7. Adequate bone marrow function:
  - a. Absolute neutrophil count (ANC)  $\geq 1.5 \times 10^9/L$  and
  - b. Hemoglobin  $\geq 10.0$  g/dL (can be corrected by growth factor or transfusion prior to first dose of study drug) and
  - c. Platelet count  $\geq 100 \times 10^9/L$
8. Adequate liver function:
  - a. Bilirubin  $\leq 1.5 \times$  upper limit of normal (ULN) except for unconjugated hyperbilirubinemia or Gilbert's syndrome
  - b. Alkaline phosphatase (ALP), alanine aminotransferase (ALT), and aspartate aminotransferase (AST)  $\leq 3 \times$  ULN ( $\leq 5 \times$  ULN if subject has liver metastases). If ALP is  $> 3 \times$  ULN (in the absence of liver metastases) or  $> 5 \times$  ULN (in the presence of liver metastases) AND subjects are also known to have bone metastases, the liver-specific ALP must be separated from the total and used to assess the liver function instead of the total ALP.
9. Voluntary agreement to provide written informed consent and the willingness and ability to comply with all aspects of the protocol.

### 9.3.2 Exclusion Criteria

Subjects who meet any of the following criteria will be excluded from this study:

1. Predominant clear cell RCC.
2. Prior anticancer chemotherapy or targeted therapy for advanced nccRCC.
3. Prior exposure to lenvatinib or mTOR inhibitor.
4. Known intolerance to lenvatinib, everolimus (or other rapamycin derivatives), or any of the excipients.
5. Major surgery performed within 3 weeks prior to the first dose of study drugs or scheduled for major surgery during the study.
6. Gastrointestinal malabsorption, gastrointestinal anastomosis, or any other condition that might affect the absorption of lenvatinib or everolimus.
7. Subjects having  $> 1 +$  proteinuria on urine dipstick testing will undergo 24 hour urine collection for quantitative assessment of proteinuria. Subjects with urine protein  $\geq 1$  g/24 hours will be ineligible.
8. Fasting total cholesterol  $>300$  mg/dL (or  $>7.75$  mmol/L) or fasting triglycerides level  $>2.5 \times$  ULN. NOTE: these subjects can be included after initiation or adjustment of lipid-lowering medication.
9. Uncontrolled diabetes as defined by fasting glucose  $> 1.5$  times the ULN. NOTE: In case this threshold is exceeded, these subjects can only be included after initiation or adjustment of glucose-lowering medication.
10. Known history of, or any evidence of, interstitial lung disease or active noninfectious pneumonitis.
11. Significant cardiovascular impairment: History of (a) congestive heart failure greater than New York Heart association (NYHA) (Appendix 4) Class II, (b) unstable angina, (c) myocardial infarction (d) stroke, or (e) cardiac arrhythmia associated with hemodynamic instability within 6 months of the first dose of study drugs.
12. Prolongation of QTcF interval to  $>480$  msec.
13. Known history of human immunodeficiency virus (HIV) positive.
14. Known active hepatitis B (eg, hepatitis B surface antigen [HBsAg] reactive) or hepatitis C (eg, hepatitis C virus [HCV] RNA detected).
15. Clinically significant hemoptysis or tumor bleeding within 2 weeks prior to the first dose of study drug.
16. Subjects with central nervous system (CNS) (eg, brain or leptomeningeal) metastases.
17. Other active malignancy (except definitively treated melanoma in-situ, basal or squamous cell carcinoma of the skin, or carcinoma in-situ of the cervix or bladder) within past 24 months.
18. Females who are breastfeeding or pregnant at Screening or Baseline (as documented by a positive beta-human chorionic gonadotropin [ $\beta$ -hCG] or human chorionic gonadotropin [hCG] test with a minimum sensitivity of 25 IU/L or equivalent units of

$\beta$ -hCG or hCG). A separate baseline assessment is required if a negative screening pregnancy test was obtained more than 72 hours before the first dose of study drug.

19. Females of childbearing potential who:

- Had unprotected sexual intercourse within 30 days before study entry and who do not agree to use a highly effective method of contraception (eg, total abstinence, an intrauterine device, a double-barrier method [such as condom plus diaphragm with spermicide], a contraceptive implant, an oral contraceptive, or have a vasectomized partner with confirmed azoospermia) throughout the entire study period or for 28 days after study drug discontinuation.
- Are currently abstinent, and do not agree to use a double-barrier method (as described above) or refrain from sexually active during the study period or for 28 days after study drug discontinuation.
- Are using hormonal contraceptives but are not on a stable dose of the same hormonal contraceptive product for at least 4 weeks before dosing and who do not agree to use the same contraceptive during the study or for 28 days after study drug discontinuation.
- Are using oral hormonal contraceptives and who do not agree to add a barrier method.
- (NOTE: All females will be considered to be of childbearing potential unless they are postmenopausal [amenorrheic for at least 12 consecutive months, in the appropriate age group, and without other known or suspected cause] or have been sterilized surgically [ie, bilateral tubal ligation, total hysterectomy, or bilateral oophorectomy, all with surgery at least 1 month before dosing]).

20. Males who have not had a successful vasectomy (confirmed azoospermia) or they and their female partners do not meet the criteria above (ie, not of childbearing potential or practicing highly effective contraception throughout the study period or for 28 days after study drug discontinuation). No sperm donation is allowed during the study period or for 28 days after study drug discontinuation.

21. Evidence of clinically significant disease (eg, cardiovascular, respiratory, gastrointestinal, renal, or infectious disease) that in the opinion of the investigator(s) could affect the subject's safety or interfere with the study assessments.

22. Any medical or other condition that in the opinion of the investigator(s) would preclude the subject's participation in a clinical study.

23. Active and current use of illegal recreational drugs.

24. Currently enrolled in another interventional clinical study or used any investigational drug or device within the past 28 days preceding informed consent.

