18. Females who are breastfeeding or pregnant at Screening or Baseline (as documented by a positive beta-human chorionic gonadotropin [ $\beta$ -hCG] or human chorionic gonadotropin [hCG] test with a minimum sensitivity of 25 IU/L or equivalent units of  $\beta$ -hCG or hCG). A separate baseline assessment is required if a negative screening pregnancy test was obtained more than 72 hours before the first dose of study drug.
19. Females of childbearing potential who:
  - Had unprotected sexual intercourse within 30 days before study entry and who do not agree to use a highly effective method of contraception (eg, total abstinence, an intrauterine device, a double-barrier method [such as a condom plus diaphragm with spermicide], a contraceptive implant, an oral contraceptive, or have a vasectomized partner with confirmed azoospermia) throughout the entire study period and for 28 days after study drug discontinuation.
  - Are currently abstinent, and do not agree to use a double-barrier method (as described above) or refrain from being sexually active during the study period or for 28 days after study drug discontinuation.
  - Are using hormonal contraceptives but are not on a stable dose of the same hormonal contraceptive product for at least 4 weeks before dosing and who do not agree to use the same contraceptive during the study or for 28 days after study drug discontinuation.
  - Are using oral hormonal contraceptives and who do not agree to add a barrier method.
  - (NOTE: All females will be considered to be of childbearing potential unless they are postmenopausal [amenorrheic for at least 12 consecutive months, in the appropriate age group, and without other known or suspected cause] or have been sterilized surgically [ie, bilateral tubal ligation, total hysterectomy, or bilateral oophorectomy, all with surgery at least 1 month before dosing]).
20. Males who have not had a successful vasectomy (confirmed azoospermia) or they and their female partners do not meet the criteria above (ie, not of childbearing potential or practicing highly effective contraception throughout the study period or for 28 days after study drug discontinuation). No sperm donation is allowed during the study period and for 28 days after study drug discontinuation.

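### Exclusion criterion 20 literally bars every man without a vasectomy, and the connectors and 28-day wording in criteria 19 and 20 need reconciling

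*Protocol*

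**What the plan says.** Section 9.3.2 opens with the rule that joins the list: "Subjects who meet any of the following criteria will be excluded from this study". Section 9.3 adds that such subjects may not receive study drug.

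**Criterion 20 (men).** The exclusion covers "Males who have not had a successful vasectomy (confirmed azoospermia) or they and their female partners do not meet the criteria above". A parenthesis explains the criteria meant: "not of childbearing potential or practicing highly effective contraception throughout the study period or for 28 days after study drug discontinuation". The Synopsis uses the same *or* between the two limbs.

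**Criterion 19 (women of childbearing potential).** There are four bullets:
- The first covers those who "Had unprotected sexual intercourse within 30 days before study entry and who do not agree to use a highly effective method of contraception".
- The second begins "Are currently abstinent, and do not agree to use a double-barrier method" and reaches only women who are abstinent now.
- The third covers users of hormonal contraception who have not been stable on one product "for at least 4 weeks before dosing and who do not agree to use the same contraceptive".
- The fourth covers users of oral hormonal products who will not add a barrier.

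**Period covered.** For the first bullet of criterion 19, the Synopsis has "throughout the entire study period and for 28 days after study drug discontinuation" and Section 9.3.2 has "throughout the entire study period or for 28 days after study drug discontinuation". The sperm-donation sentence of criterion 20 differs in the same way. The second and third bullets of criterion 19 and the parenthesis of criterion 20 say *or* in both places.

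**The concern.** In a list where any one criterion excludes, the connector inside a criterion decides who may enter. In criterion 20 an *or* between two negative limbs makes the first limb sufficient alone, so the partner and contraception route in the parenthesis is closed to the men who would need it. In criterion 19 an *and* between two limbs makes refusal excluding only when a second condition also holds, so some women who refuse fall outside every bullet.

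A site that follows criterion 20 to the letter turns away men whom its parenthesis shows it meant to admit, in a trial of about 31 subjects with a rare cancer. A site that follows the evident intent enrols men who fail the written criterion. About 8 sites may resolve this differently. For women, criteria 19 and 20 are the only places where the protocol states a contraception rule, so a gap there is not filled by a specific rule elsewhere.

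**Working it through.** The plan gives no figure on this point. The check is to read the connectors literally and list the outcomes.

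**1. Criterion 20.** Let V = confirmed vasectomy and P = partner or contraception criteria met.
- As written: excluded = (not V) or (not P).
- With the connector changed: excluded = (not V) and (not P).

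V and P are not independent. The first bullet of criterion 19 lists a partner with a confirmed vasectomy among the highly effective methods, so a man with V in effect already has P. The combination of V without P is essentially empty, which leaves three coherent situations:

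| Situation | As written (*or*) | With *and* |
|---|---|---|
| Vasectomy (P follows) | eligible | eligible |
| No vasectomy, P met | **excluded** | eligible |
| No vasectomy, P not met | excluded | excluded |

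Eligible: 1 of 3 as written, 2 of 3 with *and*. Only the middle row changes, and it is the row the parenthesis describes. Under *or*, the second limb excludes nobody whom the first has not already excluded.

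**2. Criterion 19.** Take a woman of childbearing potential who refuses every agreement asked of her.
- Sexual activity has three states: unprotected intercourse in the past 30 days, currently abstinent, or active without unprotected intercourse.
- Hormonal use has five states: none, or a hormonal method that is stable or not stable and oral or not oral (1 + 2 × 2).
- This gives 3 × 5 = 15 profiles.

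Results:
- Unprotected intercourse: all 5 excluded by the first bullet.
- Abstinent: all 5 excluded by the second bullet.
- Active without unprotected intercourse: the two not-stable hormonal states are excluded by the third bullet, and stable oral use by the fourth. Two profiles remain: no hormonal method (for example a single barrier), and a stable non-oral hormonal product that she will not continue.

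Excluded: 5 + 5 + 3 = 13 of 15. Not caught: 2 of 15. These are logical profiles, not expected proportions of women.

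**3. The 28-day period.**

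| Place | Synopsis | Section 9.3.2 |
|---|---|---|
| Criterion 19, first bullet | and | or |
| Criterion 19, second bullet | or | or |
| Criterion 19, third bullet | or | or |
| Criterion 20, parenthesis | or | or |
| Criterion 20, sperm donation | and | or |

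In the parenthesis of criterion 20, *or* read literally lets contraception in either period suffice. In the first bullet of criterion 19, failing to agree to both periods is a wider exclusion than failing to agree to either. In the sperm-donation sentence, ordinary English gives much the same prohibition either way, so that difference is textual. Section 9.5.4.2 requires reporting of conceptions before the last visit or within 28 days of last treatment, so the protocol itself treats both periods as relevant.

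**The case against.** The strongest reply is that the intent of criterion 20 can be read from its own parenthesis, that sites will probably apply it sensibly, and that this is minor drafting. The point about intent stands, and it is why the correction is safe. It does not make the written rule right: the wording is the same in both places, and Section 9.3 bars any subject who meets an exclusion from study drug.

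Several stronger readings are tempting and are not supported:
- *A vasectomized man whose partner does not meet the criteria is also shut out.* A confirmed vasectomy is itself a listed method, so counting that as a separate case inflates the effect.
- *A stated number of subjects is wrongly excluded.* The documents give neither a sex split nor the share of men without a vasectomy who meet the partner criteria. No count can be derived.
- *Any woman who refuses highly effective contraception can enter.* Only the two profiles above escape; the other 13 are excluded.
- *Fetal exposure is unaddressed.* Criterion 18 excludes pregnancy, with a repeat test if the negative result is more than 72 hours old. Section 9.5.4.2 requires prompt reporting and withdrawal of a subject who becomes pregnant. Inclusion criterion 9 and exclusion criterion 22 are general backstops. None of these is a contraception rule, but the risk is not ignored.
- *The Synopsis consistently says* and. It does so in two of the five places.
- *The right wording of the first and third bullets of criterion 19 is evident.* It is not. Joining the third bullet's limbs with *or*, for example, would newly exclude a woman who recently started a product and will stay on it, and nothing in the text shows that this was meant.

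**Conclusion.** The point holds in three parts of unequal weight.

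1. Criterion 20 gives a wrong result if followed: every man without a vasectomy is excluded and the parenthesis has no effect. This rests only on the literal text and the any-criterion rule.
2. The period wording conflicts between the Synopsis and Section 9.3.2 in two places, and in the other three it is the looser *or* in both.
3. Criterion 19 leaves two narrow profiles of refusing women uncaught. This assumes a literal reading of the bullets and no help from the general backstops.

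The wording should be corrected. It concerns eligibility and safety text only: the Simon design, the endpoints and the analyses do not depend on it.

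**What to change.** - **Criterion 20, Synopsis and Section 9.3.2:** replace the *or* between the vasectomy limb and the partner limb with *and*, so that the route in the parenthesis operates.
- **Period:** state the contraception and sperm-donation periods unambiguously and identically in all five places, in both sections.
- **Criterion 19, first and third bullets:** the sponsor should reconcile the connectors with the criterion's evident purpose and decide how the two uncaught profiles are to be treated. Which contraception rule applies is the sponsor's clinical decision.

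The first two changes are wording only and add no procedure and no subject. They still need a protocol amendment with IRB/IEC review under Sections 5.1 and 11.1. Any tightening of criterion 19 would be a substantive eligibility change and could exclude some women who can now enter.
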